
Session 6: Review and maintaining changes (One alteration: Open discussion about maintaining change in the context of other menopause-related issues or topics that were covered in sessions 1-5. Other related menopause issues may include topics such as weight changes, sexual functioning, and/or cognitive functioning. The group may discuss the challenges of maintaining change due to mood and/or anxiety disorders. The PI will facilitate this topic in lieu of maintaining change in the context of breast cancer. The group may chose topics for part of the final session as stated in the manual.

Study sessions will be audio recorded to assess reliability of following the treatment manual. The study sessions will be randomly reviewed by another study staff member to ensure quality control and fidelity will be verified by a checklist provided by [name].

End of Study (week 6): All participants will be asked to complete the same assessments completed at baseline. They will be asked to complete the following self-rated assessments: Hot Flush Frequency and Problem Rating Scale (HFFPRS), Hot Flash Belief Scale (HFBS), Menopause Representation Questionnaire (MRQ), Hot Flash Related Daily Interference Scale (HFRDIS), Snaith-Hamilton Pleasure Scale (SHAPS), Quick Inventory of Depression Symptomatology-Self Report (QIDS-SR16) and the Short-Form Couple Conflicts Scale (CTS2S). All participants will also be evaluated by clinician-rated assessments using the Montgomery Asberg Depression Rating Scale (MADRS), the Structured Interview for the Hamilton Anxiety Rating Scale (SIGH-A), the Young Mania Rating Scale (YMRS), and the Perceived Stress Scale-10 (PSS-10). All participants will be weighed at their end of study visit.

The data can be collected immediately after the end of the last study session or within 2 days of the last study session. End of Study assessments can be done in person, via e-mail, or over the phone.

The Hot Flush Weekly Diary will be collected each week.

Study Assessments

Demographics: including date of birth, race, ethnicity and smoking status

Medical and Treatment History: including date of last menstrual period, number of menstrual periods in the past year, and treatment received to treat vasomotor and/or mood symptoms.

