The Structured Interview for the Hamilton Anxiety Rating Scale (SIGH-A): This is a 14-item clinician-rated measure designed to assess the severity of anxiety.

Young Mania Rating Scale (YMRS): This is an 11-item clinician rated instrument designed to quantify severity of participant’s current symptoms of mania

BMI: A standard BMI calculator will be utilized for height and weight.

Table 1: Study Procedures Schedule

	Screening	TX(1) Baseline	TX(2)	TX(3)	TX(4)	TX(5)	TX(6) End of Intervention
Weeks		0	1	2	3	4	5
Visit	1	2	3	4	5	6	7
Intervention		X	X	X	X	X	X
Clinician Rated Assessments							
Demographics and Height	X						
Weight	X	X					X
Tracking and Documentation of Menstrual Cycles	X						
MINI	X						
MADRS	X	X					X
YMRS	X	X					X
SIGH-A	X	X					X
Concomitant Medications	X	X	X	X	X	X	X
Patient Rated Assessment							
QIDS	X	X	X	X	X	X	X

PSS	X	X					X
The Hot Flush Weekly Diary		X	X	X	X	X	X
HFFPRS		X					X
MRQ		X					X
HFBS		X					X
HFRDIS		X					X
SHAPS		X					X
CTS2S		X					X
Managing Menopausal Symptoms: Evaluation of Groups							X

Medication regimens to treat their DSM-V diagnoses will be encouraged to continue in order to determine if the CBGT accounted for any change in symptoms. Changes to medications during study participation will not be permitted. All concomitant medications taken during the study will be documented, including information on the indication, dosing, and dates of administration.

Efficacy & Data Analysis

Statistical Analysis:

Descriptive statistics will be used to describe demographic and clinical variables. This includes means and standard deviations for continuous variables and number and percentages for categorical variables. Difference in outcome measures from baseline to post-treatment will be determined by a matched-pairs *t*-test. Regression analysis will be used to assess the significance of the covariates on the differences of the 3 outcome variables. The significance of the race covariate in the regression models will be of special interest to the study. Statistical significance will be based on a Type I error rate of 0.05 for all statistical tests (two-tailed). Since this is an exploratory study no adjustment will be made for multiple comparisons.

Sample size determination.

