For a two-tailed test, setting $\alpha = 0.017$ to simultaneously account for the 3 outcome variables and assuming the dropout rate = 20%, a total sample size of 60 will provide at least 80% power for detecting a medium effect size (Cohen's $d = 0.5$) in difference in outcome measure from baseline to post-treatment. A total sample size of 30 using these parameters would enable the detection of a large effect size (Cohen's $d = 0.8$).

Protecting Patient Privacy: Study information is collected in a private office by the research coordinator and study doctor. Discussions regarding participant information or patient care will be restricted to private offices and involvement will be limited to study related staff.

Prior to the participation, all participants will be asked to agree to maintain the confidentiality of all members of the group by signing the ICF. Participants will be reminded of this agreement at each group session.

Protecting Data Confidentiality: Patient medical records are stored electronically, in Ambulatory EMR (aEMR), and are password protected. Only investigators and staff involved with the study have access to this information. All study participants are assigned a study ID. This ID is composed of a number, assigned sequentially, and the participant's initials. This identification code will take the place of a participants name on all study documents with the exception of the consent form, HIPAA authorization, and study participant ID log, all of which

will be stored separately from other study related documents in order to maintain patient confidentiality. All paper source documents and Case Report Forms (CRFs) will be stored in locked offices, and will only be listed with the study ID number and no identifying information. Only study staff will have access to the source documents and CRFs, including REDCap. For additional information on REDCAP, see “Digital Data Collection of Patient Assessments” section on pages 10-11. In order to provide additional confidentiality protection for this information, we will obtain a Certificate of Confidentiality from the National Institutes of Health.

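### Both planned analyses of change use only women with baseline and end-of-study values, so with the assumed 20% dropout the effectiveness result describes completers and may be biased in either direction

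*Combined protocol and SAP*

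**What the plan says.** Under Efficacy & Data Analysis, Statistical Analysis: "Difference in outcome measures from baseline to post-treatment will be determined by a matched-pairs" t-test. The predictor analysis uses the same quantity: "Regression analysis will be used to assess the significance of the covariates on the differences of the 3 outcome variables". The race coefficient in that regression is singled out as of particular interest.

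Under Sample size determination, dropout appears once: "assuming the dropout rate = 20%, a total sample size of 60" is said to give the stated power, after "setting $\alpha = 0.017$ to simultaneously account for the 3 outcome variables". It is used only to size the study.

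Table 1 schedules the three outcome scales (HFFPRS, HFRDIS, MRQ) at baseline and at the last session only. The diary and the QIDS are weekly: "The Hot Flush Weekly Diary will be collected each week". The End of Study section asks all participants for the closing assessments and allows them in person, by e-mail or by phone. It has no line about women who have stopped attending.

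The document defines no analysis set, imputation or likelihood-based method, sensitivity analysis, or comparison of completers with dropouts.

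**The concern.** A woman who leaves and returns no end-of-study forms has no difference score, so she enters neither the t-test nor the regression. Her baseline scores are then not used in any analysis of change.

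Aim 2 concerns effectiveness in Black and White women with bipolar disorder or major depressive disorder. It is not limited to those who finish six sessions. If women who leave would have changed by a different amount, the completer mean does not answer Aim 2. The race coefficient is exposed in the same way if dropout differs by race and by response.

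**Working it through.** **Inputs from the document.** N = 60; dropout 20%; two-sided alpha 0.017 for sizing; d = 0.5 in SD units of within-woman change; target power at least 80%. No SD, pre-post correlation or dropout pattern is given.

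**1. The plan's own figure.** Pairs = 60 × 0.80 = 48. Paired t-test: noncentrality = d√n = 0.5 × √48 = 3.46, with 47 degrees of freedom. Exact power at alpha 0.017 is 83.4% (normal approximation 85.9%), so the stated figure reproduces. The smallest number of pairs giving 80% is 45, or 45/0.8 = 56.25, hence 57 enrolled. The sizing is sound and already counts completers only. (The analysis section uses alpha 0.05, where 48 pairs give 92.4%. That difference is a separate matter.)

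**2. Bias of the completer mean.** With 20% lost, all-enrolled mean = 0.8 × (completer mean) + 0.2 × (dropout mean). So bias = 0.2 × (completer mean − dropout mean). For a completer mean of 0.50 SD:

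| Assumed dropout mean (SD) | All-enrolled mean (SD) | Completer bias (SD) |
|---|---|---|
| −0.50 | 0.30 | +0.20 |
| 0 | 0.40 | +0.10 |
| 0.50 | 0.50 | 0 |
| 1.00 | 0.60 | −0.10 |

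**3. Would using all available data help?** Simulation with a true mean change of 0.50 SD, about 20% dropout and an assumed pre-post correlation of 0.6. The all-data estimate adjusts for baseline and uses every woman's baseline value, which is what a likelihood-based model of the two time points exploits.

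| Assumed dropout mechanism | Completers | All-data |
|---|---|---|
| More severe at baseline leave (log-odds slope 0.8 per SD) | about 0.43 | 0.50 |
| Less severe at baseline leave (same slope) | about 0.56 | 0.50 |
| Non-responders leave (slope 1.0 per SD of change) | about 0.67 | about 0.64 |

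The standard error of a completer mean is 1/√48 = 0.144 SD. The baseline-dependent bias (0.06 to 0.07) is therefore under half a standard error. The non-responder bias (0.67 − 0.50 = 0.17) is 0.17/0.144 = 1.2 standard errors, and the model removes only about 0.03 of it.

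**4. Power of a zero-change sensitivity analysis.** Assume dropout unrelated to response, completer change with mean 0.5 and SD 1, and 20% set to zero. Mean = 0.8 × 0.5 = 0.40. Variance = 0.8 × (1 + 0.25) − 0.40² = 0.84. Standardised effect = 0.40/√0.84 = 0.436. With n = 60 and alpha 0.017, power is 81.9%. Direct simulation with exactly 12 zeros gives 83.4%.

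**The case against.** Four points on the other side have force.

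- **Exclusion is not a stated rule.** A reader might infer that the plan orders dropouts to be deleted. It does not. Deletion is what the named test does when no missing-data method is given.
- **Twenty per cent is a sizing assumption.** A reader might infer that 12 women are expected to lack end-of-study data. Leaving therapy need not mean missing forms, since all participants are asked for them and e-mail or phone is allowed. The real loss may be smaller or larger.
- **The better model is limited.** Where it works, the bias is under half a standard error and rests on an assumed slope and correlation. Where the bias is larger, it barely helps. A two-time-point model also leaves the diary and QIDS unused, so those weekly data are no argument for it; only multiple imputation could use them.
- **The study is single-arm and exploratory, with feasibility as Aim 1.** That bears on how firmly the result will be read. The plan, however, uses its exploratory status only to justify making no multiplicity adjustment. It does not turn a completer mean into the mean for everyone treated. The lack of a comparator is a separate threat that none of this removes.

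These points limit the wording and the size. They do not supply the missing analysis set or method.

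**Conclusion.** The concern holds in limited form. As written, the effectiveness and predictor results apply to women with both values, and the plan gives no way to see how far that departs from Aim 2. Each 0.50 SD gap between completers and dropouts moves the estimate by 0.2 × 0.50 = 0.10 SD at 20% loss. There is no bias if the two groups change equally on average.

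Two stronger readings are not supported. The study is not underpowered because of dropout: 48 pairs give 83.4%. Nor can the direction be predicted. It seems natural to suppose that completers flatter the therapy, but the document has no data on who leaves, and women leaving because they improved would push the other way.

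The simulated figures illustrate assumed mechanisms and are not forecasts. The points that need no assumption are the dependence on paired values, the schedule of the three outcomes, and the absence of any missing-data provision.

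**What to change.** 1. **Statistical Analysis:** analyse each outcome in all women with a baseline value, using a likelihood-based repeated-measures model of the baseline and end-of-study values. Multiple imputation is an alternative and could also draw on the weekly diary and QIDS. Apply the same approach to the predictor analysis. Keep the paired t-test as a supportive completer analysis.
2. **Sensitivity analysis:** repeat with change set to zero for women without end-of-study data. This is needed because the model in item 1 does not remove bias when dropout depends on the outcome. Power is about 82% with n = 60 at alpha 0.017 if dropout is unrelated to response.
3. **End of Study section:** state that the end-of-study forms, already allowed by e-mail or phone, are also sought from women who stop attending. Report the number of dropouts and baseline scores by completion status.

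Cost: some added wording, slightly more analysis work, some contact with women who have left, and possibly a smaller estimated effect. No new visits, instruments or participants are needed.
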